1.2.1.1 Pharmacokinetics Data for BGB-290-AU-002

In the first-in-human Phase 1 study, interim pharmacokinetics (PK) data of pamiparib showed that pamiparib is rapidly absorbed and eliminated after oral administration. The maximum serum concentration and the drug exposure area under the concentration-time curve (AUC) increased in a nearly dose proportional manner from 2.5 to 120 mg twice a day both after the single-dose administration and at steady-state. The terminal half-life was determined to be approximately 13 hours, with a range of 5.5 to 34 hours. At steady-state, from 2.5 to 120 mg twice a day, drug exposure was increased in a dose-dependent manner.

A total of 13 patients in Study BGB-290-AU-002 contributed to serial plasma samples at predose, 0.5, 1, 2, 4, 7, 24 and 48 hours after a single 60 mg dose of pamiparib, either fasted or with high-fat breakfast, each followed by a 5-day washout for food-effect PK investigation.

[figure not shown]
When pamiparib was administered with food, a reduction of 15% in AUC and 41% in C_{max} was observed, along with a delay of T_{max} from 2 to 7 hours.

The 15% reduction in AUC is not considered to be clinically relevant and falls well within the variability of pamiparib exposure of approximately 50% coefficient of variation. Therefore, food restrictions are not required with pamiparib administration.

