2.2 Secondary Objectives

The secondary objectives of the study are:

- to evaluate the safety and tolerability of pamiparib when coadministered with rifampin or itraconazole/fluconazole in cancer patients
- to further investigate the tolerability of oral pamiparib in patients with advanced solid tumors (Extension Phase).

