4.2 Discussion of Study Design

This is an open label, non-randomized study designed to evaluate the effect of rifampin (a strong CYP3A inducer) and itraconazole (a strong CYP3A inhibitor) on the PK of pamiparib in cancer patients.

A parallel-group design has been selected due to the potential for carryover of CYP induction following rifampin dosing, which can remain for several weeks following cessation of dosing ([Reitman, et al](#)) and would prolong the study duration to a significant degree if a crossover design were utilized.

For the Core Phase, the total duration of study participation for each patient (from Screening through the EOT Visit) is anticipated to be approximately 48 days.

Patients may participate in the Extension Phase during which they will receive pamiparib monotherapy until disease progression, unacceptable toxicity, withdrawal of consent, or any other reason for discontinuation.

Rationale for selection of the pamiparib dose:

A dose of 60 mg pamiparib has been chosen for the induction portion of the study (Part A), as 60 mg twice daily was administered to patients in Phase 1 study BGB-290-AU-002 and was well tolerated.

A dose of 20 mg pamiparib has been chosen for the inhibition portion of the study (Part B), as it is one-sixth of 120 mg, where 120 mg BID is the highest dose administered in the phase I trial. With an observed rate of accumulation of approximately 2-fold, this gives an approximate of 12-fold margin, which should be sufficient to cover the plasma exposure increase due to complete blockade of CYP3A by itraconazole after a single-dose administration of 20 mg pamiparib. In addition, 20 mg is the lowest dose strength of pamiparib.

Given the objective of determining whether a CYP3A inducer or inhibitor has an effect on the BGB-290 PK, these doses are considered to be adequate to achieve study objectives with minimal risk to subjects.

Rationale for selection of the rifampin and itraconazole doses:

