8.2.5 Physical Examination

Complete and limited physical examinations will be performed at the timepoints specified in the Schedule of Assessments in [Appendix 1](#). A complete physical examination includes a review of the following systems: head/neck/thyroid; eyes/ears/nose/throat; respiratory; cardiovascular; lymph nodes; abdomen; skin; musculoskeletal; and neurological. A limited physical examination includes an assessment of the patient's general appearance, skin, thorax/lungs, cardiovascular, and abdomen.

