12.11 Sponsor Responsibilities

12.11.1 Protocol Modifications

Protocol modifications, except those intended to reduce immediate risk to study patients, may be initiated only by BeiGene. All protocol modifications must be submitted to regulatory authorities and the IRB/IEC together with, if applicable, a revised model ICF in accordance with local requirements. As applicable by local requirements, written documentation of regulatory authorities, IRB/IEC and required study center approval must be obtained by the sponsor before changes can be implemented.

Information on any change in risk and /or change in scope must be provided to patients already actively participating in the study, and they must read, understand and sign each revised ICF confirming his/her willingness to remain in the study.

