Allowed time window (days)		± 2	± 2	± 2		
Body Weight	X	X		X	X	
ECOG performance status		X		X	X	
Urinalysis	X				X	
Vital Signs ^a	X				X	
12-Lead ECG ^b	X				X	
Limited Physical examination ^c	X	X		X	X	X
Clinical chemistry and hematology	X	X	X	X	X	X ^j
Pregnancy test	X	X		X	X	
Pamiparib administration ^d		X (60 mg PO twice daily)				
Tumor assessments (CT or MRI scan)		X (every 8 weeks ± 7 days)				
Adverse event recording	X	X	X	X	X	X
Concomitant medication	X	X	X	X	X	X

Abbreviations: CT = computed tomography ECG = electrocardiogram; ECOG = Eastern Cooperative Oncology Group; EOT: end of treatment; MRI = magnetic resonance imaging; PO = orally.

- a. Vital Signs: Blood pressure, heart rate, and temperature must be measured after the patient has been supine for 5 minutes at Screening and EOT.
- b. Single 12-lead ECGs will be repeated once if outside the clinical reference range, or there is other clinically significant finding. Repeat ECGs will be recorded in triplicate at least 2 minutes apart. ECGs will be recorded after the patient has been supine for 5 minutes.
- c. Limited physical examination: includes assessment of general appearance and additional examination of symptomatic systems or those affected by the patient’s disease. For the follow-up visit, the limited physical examination is only to be done if this visit is conducted while the patient is attending the clinic.
- d. Dosing: Pamiparib capsules should be administered continuously from Cycle 1 Day 1 (60 mg twice daily), until patients are discontinued from treatment.
- e. Predose visit: Assessments performed in the Core Phase Follow-up visit for Part 1 may be used as the predose visit for the Extension Phase if it occurs ≤ 7days prior to the start of pamiparib treatment in Extension Phase.

- f. Cycle 3+: Cycles will continue as long as the patient is experiencing clinical benefit, or until occurrence of progressive disease (PD), unacceptable toxicity, pregnancy, death, withdrawal of consent, lost to follow-up, major protocol violation which in the opinion of the sponsor would have significant impact on the study or its outcome, start of new anticancer therapy, withdrawal by the PI, or study termination by sponsor.

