5.1.2 Secondary Objectives

- To evaluate the safety and tolerability of pamiparib when coadministered with rifampin or itraconazole in patients with advanced solid tumors
- To further investigate the safety of oral pamiparib in patients with advanced solid tumors (Extension Phase)

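### In the Extension Phase, blood pressure, pulse, temperature and 12-lead ECG are scheduled only before dosing and at End of Treatment, so no cycle visit has a planned value on 60 mg twice daily (minor).

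*Protocol*

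**What the plan says.** **Schedule.** In the Extension Phase table of Protocol Appendix 1, the vital-signs and 12-lead ECG rows are marked at the Predose visit and at EOT. They are blank at Day 1 and Day 15 of Cycles 1 and 2, at Day 1 of later cycles, and at Safety Follow-up. Footnote a says that blood pressure, heart rate and temperature "must be measured after the patient has been supine for 5 minutes at Screening and EOT". SAP Appendix 2 carries the same table and footnote. Footnote i places the Cycle 1 Day 1 assessments before the first Extension dose. Footnote g puts EOT within 7 days after the last dose, and Protocol 8.3 asks for it as soon as possible.

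**Purpose.** Vital signs and ECG parameters are secondary endpoints (Protocol 3.2). The Extension objective in SAP 5.1.2, as in the protocol synopsis, is "To further investigate the safety of oral pamiparib in patients with advanced solid tumors (Extension Phase"). Protocol 2.2 words it as "to further investigate the tolerability of oral pamiparib in patients with advanced solid tumors (Extension Phase").

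**Use of the data.** SAP 18.1.4 and 18.1.5 summarize vital signs and ECG at scheduled times. SAP 9.1.5 lists unscheduled values but leaves them out of descriptive statistics, except for baseline and CTCAE shift tables. SAP 18.1 includes weight among the vital signs. Protocol Table 2 requires pamiparib to be held, and stopped if a cardiologist confirms the finding, for QTcF above 500 msec or a QTc change above 60 msec.

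**Other monitoring.** Protocol 8.2.3 and 8.2.4 take their timing from Appendix 1 and allow extra vital signs or ECGs when clinically appropriate.

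**The concern.** The Extension Phase is where patients take 60 mg twice daily for as long as they benefit. The Core Phase has timed vital signs and a 2-hour postdose ECG, but after single doses of 60 mg (Part A) or 20 mg (Part B). Safety at steady state on twice-daily dosing is therefore a question for the Extension, yet two of its secondary endpoints are planned only before dosing starts and after it has normally stopped.

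Two things follow. First, the Extension tables for blood pressure, pulse, temperature and ECG may compare a pre-treatment value with a value taken after most of the drug has gone. A discretionary on-treatment value appears in the listings but not in the descriptive statistics. Second, the Table 2 QTc rule is written for patients on treatment, but no scheduled ECG during treatment can set it off. An EOT ECG normally comes too late for a hold to help.

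**Working it through.** The plan gives no figure to reproduce here. The check is a count of scheduled cells, followed by simple kinetics.

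**1. Cycle visits after first dosing.** Cycle 1 Day 1 is predose and is not counted. One cycle leaves Cycle 1 Day 15, which is 1 visit. For N ≥ 2 cycles the visits are Cycle 1 Day 15, Cycle 2 Day 1, Cycle 2 Day 15 and one Day 1 visit for each later cycle: 3 + (N − 2) = N + 1.

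| Cycles | Visits after first dosing | Blood pressure, pulse, temperature or ECG planned | Weight and limited physical examination planned (N − 1) | Laboratory tests and AE review planned |
|---|---|---|---|---|
| 1 | 1 | 0 | 0 | 1 |
| 2 | 3 | 0 | 1 | 3 |
| 4 | 5 | 0 | 3 | 5 |
| 6 | 7 | 0 | 5 | 7 |

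**2. Are the cycle visits at steady state?** Protocol 1.2.1.1 states: "The terminal half-life was determined to be approximately 13 hours, with a range of 5.5 to 34 hours". The visit window is ±2 days, so Cycle 1 Day 15 can fall on Day 13, after 12 full days (288 h) of dosing. The fraction of steady state is 1 − 2^(−288/t½): above 99.99% at 13 h and 99.72% at 34 h. Unless dosing has been held, every cycle visit from Cycle 1 Day 15 onward is at steady state.

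**3. Does EOT stand in for an on-treatment value?** The fraction of drug remaining is 2^(−t/t½).

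| Time since last dose | t½ 5.5 h | t½ 13 h | t½ 34 h |
|---|---|---|---|
| 1 day (24 h) | 4.9% | 28% | 61% |
| 2 days (48 h) | 0.24% | 7.7% | 38% |
| 7 days (168 h) | below 0.001% | 0.013% | 3.3% |

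A prompt EOT visit can retain appreciable drug. One at the end of the 7-day window retains almost none.

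**4. Do the Core Phase single doses stand in?** Assume linear one-compartment kinetics and a 12 h interval. The ratio of steady-state AUC over one interval to first-dose AUC over 0–12 h is 1/(1 − 2^(−12/t½)): 1.28 at 5.5 h, 2.12 at 13 h and 4.61 at 34 h. Protocol 4.2 agrees with the middle value ("With an observed rate of accumulation of approximately 2-fold"). So 60 mg twice daily gives about twice the 12-hour exposure of the single 60 mg Part A reference dose, sustained over weeks.

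**The case against.** The strongest reply is that this is a considered and consistent schedule. The rows, the footnote and the SAP copy agree, and nothing in the documents requires on-treatment ECGs. Monitoring is weighted toward the toxicities reported in Protocol 1.2.1.3: nausea, vomiting, fatigue, diarrhea, anemia and neutropenia. That section reports no QT or blood-pressure signal in preliminary data on 81 patients at 2.5 to 120 mg twice daily. The Extension is optional, uncontrolled, drawn from about 24 patients and without hypothesis tests, so the listings can be read patient by patient.

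Much of this stands, and it sets the grade:

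- Chemistry (including potassium and calcium), hematology, adverse events and concomitant medication are covered at every cycle visit. A note in Table 2 adds weekly hematology for the first 3 cycles.
- A limited physical examination is planned on Day 1 visits. Protocol 8.2.5 describes it as covering "general appearance, skin, thorax/lungs, cardiovascular, and abdomen"; the Extension footnote is narrower and "includes assessment of general appearance and additional examination of symptomatic systems". Either can prompt a discretionary ECG or blood-pressure reading.
- Clinically significant abnormalities are recorded as adverse events (Protocol 9.1.5) and so reach the tables by that route.

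Three stronger readings are tempting, and the documents do not support them. A reader might infer that no Extension value can ever be on drug. But Protocol 8.3 lets the visit that documents progression serve as EOT, and a next-day EOT retains 28% at the 13 h half-life. A reader might infer that the SAP's whole vital-signs category lacks on-treatment data. But weight belongs to that category and is scheduled on Day 1 of each cycle. A reader might infer a hidden cardiac risk. The documents show none, and the Investigator's Brochure, which holds the fuller profile, is not available here.

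The reply does not explain why blood pressure, pulse and temperature are left off visits that patients already attend.

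**Conclusion.** The point holds as a minor monitoring and data gap. Blood pressure, pulse, temperature and ECG are planned at none of the N + 1 cycle visits after first dosing (N ≥ 2), although those visits are at steady state. The Extension summaries of these measures have no assured on-treatment value, and during treatment the QTc rule depends on a discretionary ECG.

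The visit counts come directly from the schedule table. The residual-drug figures assume first-order elimination at the reported half-lives, and the exposure ratio also assumes linear one-compartment kinetics. The conclusion does not depend on the exact values, since steady state by Cycle 1 Day 15 holds across the whole half-life range.

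This is neither a contradiction between protocol and SAP nor a demonstrated bias. The primary PK objectives are unaffected.

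**What to change.** 1. In the Extension table of Protocol Appendix 1 and in SAP Appendix 2, mark vital signs at Cycle 1 Day 15, at Cycle 2 Day 1 and Day 15, and at Day 1 of Cycle 3 onward. Amend footnote a to name these visits. Because they become scheduled times, SAP 18.1.4 will then summarize them without further change.
2. Optionally, add one ECG at Cycle 1 Day 15 or Cycle 2 Day 1, about 2 hours postdose as in the Core Phase. The timing matters: at the 13 h half-life a 12-hour trough holds 2^(−12/13) = 53% of the postdose level, so an untimed ECG could miss the higher concentrations. Record the dose time and whether the dose was taken with food, because Protocol 1.2.1.1 reports that food delays Tmax from 2 to 7 hours and the Extension does not require fasting.

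**Cost.** No new visits are needed. Vital signs add a few minutes at each visit. If the ECG is adopted, planned Extension ECGs go from 2 to 3 per patient. The change needs a routine amendment; under Protocol 12.11.1, "All protocol modifications must be submitted to regulatory authorities and the IRB/IEC". If Extension dosing has already ended, the study report can state that no on-treatment values of these measures were planned.

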Appendix 2: The Response Evaluation Criteria In Solid Tumors (RECIST) Guidelines, Version 1.1

The text below was obtained from the following reference: Eisenhauer EA, Therasse P, Bogaerts J, et al. New response evaluation criteria in solid tumors: revised RECIST guideline (version 1.1). *Eur J Cancer*. 2009;45:228-247 (Eisenhauer et al, 2009).

DEFINITIONS

Response and progression will be evaluated in this study using the international criteria proposed by the Response Evaluation Criteria in Solid Tumors (RECIST) Committee (Version 1.1). Changes in only the largest diameter (unidimensional measurement) of the tumor lesions are used in the RECIST criteria. Note: Lesions are either measurable or nonmeasurable using the criteria provided below. The term “evaluable” in reference to measurability will not be used because it does not provide additional meaning or accuracy.

Measurable Disease

Tumor lesions: Must be accurately measured in at least 1 dimension (longest diameter in the plane of measurement is to be recorded) with a minimum size of:

- 10 mm by CT scan (irrespective of scanner type) and MRI (no less than double the slice thickness and a minimum of 10 mm).
- 10 mm caliper measurement by clinical exam (when superficial).
- 20 mm by chest x-ray (if clearly defined and surrounded by aerated lung).

Malignant lymph nodes: To be considered pathologically enlarged and measurable, a lymph node must be ≥ 15 mm in short axis when assessed by computed tomography (CT) scan (CT scan slice thickness recommended to be no greater than 5 mm). At baseline and in follow-up, only the short axis will be measured and followed.

Nonmeasurable Disease

All other lesions (or sites of disease), including small lesions (longest diameter ≥ 10 to < 15 mm with conventional techniques or < 10 mm using spiral CT scan), are considered nonmeasurable disease. Leptomeningeal disease, ascites, pleural, or pericardial effusion, inflammatory breast disease, lymphangitic involvement of skin or lung, abdominal masses/abdominal organomegaly identified by physical examination that is not measurable by reproducible imaging techniques are all nonmeasurable.

Bone lesions:

- Bone scan, positron-emission tomography (PET) scan, or plain films are not considered adequate imaging techniques to measure bone lesions. However, these techniques can be used to confirm the presence or disappearance of bone lesions.
- Lytic bone lesions or mixed lytic-blastic lesions, with identifiable soft tissue components, that can be evaluated by cross sectional imaging techniques such as CT or magnetic

resonance imaging (MRI) can be considered as measurable lesions if the soft tissue component meets the definition of measurability described above.

- Blastic bone lesions are nonmeasurable.

Cystic lesions:

- Lesions that meet the criteria for radiographically defined simple cysts should not be considered as malignant lesions (neither measurable nor nonmeasurable) since they are, by definition, simple cysts.
- Cystic lesions thought to represent cystic metastases can be considered as measurable lesions, if they meet the definition of measurability described above. However, if noncystic lesions are present in the same patient, these are preferred for selection as target lesions.

Lesions with prior local treatment:

- Tumor lesions situated in a previously irradiated area, or in an area subjected to other locoregional therapy, are usually not considered measurable unless there has been demonstrated progression in the lesion. Trial protocols should detail the conditions under which such lesions would be considered measurable.

Target Lesions

All measurable lesions up to a maximum of 2 lesions per organ and 5 lesions in total should be identified as target lesions and recorded and measured at baseline. Target lesions should be selected on the basis of their size (lesions with the longest diameter), be representative of all involved organ, but in addition should be those that lend themselves to reproducible repeated measurements.

Lymph nodes merit special mention since they are normal anatomical structures that may be visible by imaging even if not involved by tumor. Pathological nodes that are defined as measurable and may be identified as target lesions must meet the criterion of a short axis of ≥ 15 mm by CT scan. Only the short axis of these nodes will contribute to the baseline sum. The short axis of the node is the diameter normally used by radiologists to judge if a node is involved by solid tumor. Nodal size is normally reported as 2 dimensions in the plane in which the image is obtained (for CT scan this is almost always the axial plane; for MRI the plane of acquisition may be axial, sagittal, or coronal). The smaller of these measures is the short axis. For example, an abdominal node which is reported as being 20 mm x 30 mm has a short axis of 20 mm and qualifies as a malignant, measurable node. In this example, 20 mm should be recorded as the node measurement. All other pathological nodes (those with short axis ≥ 10 mm but < 15 mm) should be considered nontarget lesions. Nodes that have a short axis < 10 mm are considered nonpathological and should not be recorded or followed.

A sum of the diameters (longest for non-nodal lesions, short axis for nodal lesions) for all target lesions will be calculated and reported as the baseline sum diameters. If lymph nodes are to be included in the sum, then as noted above, only the short axis is added into the sum. The baseline

sum diameters will be used as reference to further characterize any objective tumor regression in the measurable dimension of the disease.

Nontarget Lesions

All other lesions (or sites of disease) including pathological lymph nodes should be identified as nontarget lesions and should also be recorded at baseline. Measurements are not required and these lesions should be followed as “present”, “absent”, or in rare cases “unequivocal progression” (more details to follow). In addition, it is possible to record multiple nontarget lesions involving the same organ as a single item on the electronic case report form (eCRF) (eg, “multiple enlarged pelvic lymph node” or “multiple liver metastases”).

GUIDELINES FOR EVALUATION OF MEASURABLE DISEASE

All measurements should be recorded in metric notation, using calipers if clinically assessed. All baseline evaluations should be performed as close as possible to the treatment start and never more than 4 weeks before the beginning of the treatment.

The same method of assessment and the same technique should be used to characterize each identified and reported lesion at baseline and during follow-up. Imaging based evaluation should always be done rather than clinical examination unless the lesion(s) being followed cannot be imaged but are assessable by clinical examination.

Clinical lesions: Clinical lesions will only be considered measurable when they are superficial and P10 mm diameter as assessed using calipers (eg, skin nodules). For the case of skin lesions, documentation by color photography including a ruler to estimate the size of the lesion is suggested. As noted above, when lesions can be evaluated by both clinical examination and imaging, imaging evaluation should be undertaken since it is more objective and may also be reviewed at the end of the trial.

Chest x-ray: Chest CT is preferred over chest x-ray, particularly when progression is an important endpoint, since CT is more sensitive than x-ray, particularly in identifying new lesions. However, lesions on chest x-ray may be considered measurable if they are clearly defined and surrounded by aerated lung.

CT, MRI: CT is the best currently available and reproducible method to measure lesions selected for response assessment. This guideline has defined measurability of lesions on CT scan based on the assumption that CT slice thickness is 5 mm or less. When CT scans have slice thickness greater than 5 mm, the minimum size for a measurable lesion should be twice the slice thickness. MRI is also acceptable in certain situations (eg, for body scans).

Ultrasound: Ultrasound is not useful in assessment of lesion size and should not be used as a method of measurement. Ultrasound examinations cannot be reproduced in their entirety for independent review at a later date and, because they are operator dependent, it cannot be guaranteed that the same technique and measurements will be taken from one assessment to the next. If new lesions are identified by ultrasound in the course of the study, confirmation by CT or MRI is advised. If there is concern about radiation exposure at CT, MRI may be used instead of CT in selected instances.

Endoscopy, laparoscopy: The utilization of these techniques for objective tumor evaluation is not advised. However, they can be useful to confirm complete pathological response when biopsies are obtained or to determine relapse in trials where recurrence following complete response (CR) or surgical resection is an endpoint.

Tumor markers: Tumor markers alone cannot be used to assess objective tumor response. If markers are initially above the upper normal limit, they must normalize for a patient to be considered in CR. Because tumor markers are disease specific, instructions for their measurement should be incorporated into protocols on a disease specific basis. Specific guidelines for both CA-125 response (in recurrent ovarian cancer) and prostate-specific antigen response (in recurrent prostate cancer), have been published. In addition, the Gynecologic Cancer Intergroup has developed CA-125 progression criteria that are to be integrated with objective tumor assessment for use in first-line trials in ovarian cancer.

Cytology, histology: These techniques can be used to differentiate between partial response (PR) and CR in rare cases if required by protocol (for example, residual lesions in tumor types such as germ cell tumors, where known residual benign tumors can remain). When effusions are known to be a potential adverse effect of treatment (eg, with certain taxane compounds or angiogenesis inhibitors), the cytological confirmation of the neoplastic origin of any effusion that appears or worsens during treatment can be considered if the measurable tumor has met criteria for response or stable disease (SD) in order to differentiate between response (or SD) and progressive disease (PD).

RESPONSE CRITERIA

Evaluation of Target Lesions

CR: Disappearance of all target lesions. Any pathological lymph nodes (whether target or nontarget) must have reduction in short axis to <10 mm.

PR: At least a 30% decrease in the sum of diameters of target lesions, taking as reference the baseline sum diameters.

PD: At least a 20% increase in the sum of diameters of target lesions, taking as reference the smallest sum on study (this includes the baseline sum if that is the smallest on study). In addition to the relative increase of 20%, the sum must also demonstrate an absolute increase of at least 5 mm.

SD: Neither sufficient shrinkage to qualify for PR nor sufficient increase to qualify for PD, taking as reference the smallest sum diameters while on study.

Lymph nodes: Lymph nodes identified as target lesions should always have the actual short axis measurement recorded (measured in the same anatomical plane as the baseline examination), even if the nodes regress to below 10 mm on study. This means that when lymph nodes are included as target lesions, the “sum” of lesions may not be zero even if CR criteria are met, since a normal lymph node is defined as having a short axis of <10 mm. Case report recorded in a separate section where, in order to qualify for CR, each node must achieve a short axis <10 mm. For PR, SD, and PD, the actual short axis measurement of the nodes is to be included in the sum of target lesions.

Target lesions that become “too small to measure”: While on study, all lesions (nodal and non-nodal) recorded at baseline should have their actual measurements recorded at each subsequent evaluation, even when very small (eg, 2 mm). However, sometimes lesions or lymph nodes which are recorded as target lesions at baseline become so faint on CT scan that the radiologist may not feel comfortable assigning an exact measure and may report them as being “too small to measure”. When this occurs it is important that a value be recorded on the eCRF. If it is the opinion of the radiologist that the lesion has likely disappeared, the measurement should be recorded as 0 mm. If the lesion is believed to be present and is faintly seen but too small to measure, a default value of 5 mm should be assigned (Note: It is less likely that this rule will be used for lymph nodes since they usually have a definable size when normal and are frequently surrounded by fat such as in the retroperitoneum; however, if a lymph node is believed to be present and is faintly seen but too small to measure, a default value of 5 mm should be assigned in this circumstance as well). This default value is derived from the 5 mm CT slice thickness (but should not be changed with varying CT slice thickness). The measurement of these lesions is potentially nonreproducible; therefore, providing this default value will prevent false responses or progressions based upon measurement error. To reiterate, however, if the radiologist is able to provide an actual measure, that should be recorded, even if it is below 5 mm.

Lesions that split or coalesce on treatment: When non-nodal lesions “fragment”, the longest diameters of the fragmented portions should be added together to calculate the target lesion sum. Similarly, as lesions coalesce, a plane between them may be maintained that would aid in obtaining maximal diameter measurements of each individual lesion. If the lesions have truly coalesced such that they are no longer separable, the vector of the longest diameter in this instance should be the maximal longest diameter for the “coalesced lesion”.

Evaluation of Nontarget Lesions

While some nontarget lesions may actually be measurable, they need not be measured and instead should be assessed only qualitatively at the time points specified in the protocol.

CR: Disappearance of all nontarget lesions and normalization of tumor marker level. All lymph nodes must be nonpathological in size (<10 mm short axis).

Non-CR/Non-PD: Persistence of one or more nontarget lesion(s) and/or maintenance of tumor marker level above the normal limits.

PD: Unequivocal progression (see comments below) of existing nontarget lesions.

When the patient also has measurable disease: In this setting, to achieve “unequivocal progression” on the basis of the nontarget disease, there must be an overall level of substantial worsening in nontarget disease such that, even in presence of SD or PR in target disease, the overall tumor burden has increased sufficiently to merit discontinuation of therapy. A modest “increase” in the size of one or more nontarget lesions is usually not sufficient to qualify for unequivocal progression status. The designation of overall progression solely on the basis of change in nontarget disease in the face of SD or PR of target disease will therefore be extremely rare.

When the patient has only nonmeasurable disease: This circumstance arises in some Phase 3 trials when it is not a criterion of trial entry to have measurable disease. The same general

concept applies here as noted above, however, in this instance there is no measurable disease assessment to factor into the interpretation of an increase in nonmeasurable disease burden. Because worsening in nontarget disease cannot be easily quantified (by definition: if all lesions are truly nonmeasurable) a useful test that can be applied when assessing patients for unequivocal progression is to consider if the increase in overall disease burden based on the change in nonmeasurable disease is comparable in magnitude to the increase that would be required to declare PD for measurable disease: ie, an increase in tumor burden representing an additional 73% increase in “volume” (which is equivalent to a 20% increase diameter in a measurable lesion). Examples include an increase in a pleural effusion from “trace” to “large”, an increase in lymphangitic disease from localized to widespread, or may be described in protocols as “sufficient to require a change in therapy”. If “unequivocal progression” is seen, the patient should be considered to have had overall PD at that point. While it would be ideal to have objective criteria to apply to nonmeasurable disease, the very nature of that disease makes it impossible to do so; therefore, the increase must be substantial.

New Lesions

The appearance of new malignant lesions denotes disease progression; therefore, some comments on detection of new lesions are important. There are no specific criteria for the identification of new radiographic lesions; however, the finding of a new lesion should be unequivocal: ie, not attributable to differences in scanning technique, change in imaging modality or findings thought to represent something other than tumor (for example, some “new” bone lesions may be simply healing or flare of preexisting lesions). This is particularly important when the patient’s baseline lesions show PR or CR. For example, necrosis of a liver lesion may be reported on a CT scan report as a “new” cystic lesion, which it is not.

A lesion identified on a follow-up trial in an anatomical location that was not scanned at baseline is considered a new lesion and will indicate disease progression. An example of this is the patient who has visceral disease at baseline and while on trial has a CT or MRI brain ordered which reveals metastases. The patient’s brain metastases are considered to be evidence of PD even if he/she did not have brain imaging at baseline.

If a new lesion is equivocal, for example because of its small size, continued therapy and follow-up evaluation will clarify if it represents truly new disease. If repeat scans confirm there is definitely a new lesion, then progression should be declared using the date of the initial scan.

While FDG-PET (PET scanning with the tracer fluorine-18 [F-18]fluorodeoxyglucose [FDG]) response assessments need additional study, it is sometimes reasonable to incorporate the use of FDG-PET scanning to complement CT scanning in assessment of progression (particularly possible “new” disease). New lesions on the basis of FDG-PET imaging can be identified according to the following algorithm:

- Negative FDG-PET at baseline, with a positive FDG-PET at follow-up is a sign of PD based on a new lesion. No FDG-PET at baseline and a positive FDG-PET at follow-up: If the positive FDG-PET at follow-up corresponds to a new site of disease confirmed by CT, this is PD. If the positive FDG-PET at follow-up is not confirmed as a new site of

disease on CT, additional follow-up CT scans are needed to determine if there is truly progression occurring at that site (if so, the date of PD will be the date of the initial abnormal FDG-PET scan). If the positive FDG-PET at follow-up corresponds to a preexisting site of disease on CT that is not progressing on the basis of the anatomic images, this is not PD.

Evaluation of Best Overall Response

The best overall response is the best response recorded from the start of the study drug treatment until the end of treatment taking into account any requirement for confirmation. On occasion a response may not be documented until after the end of therapy so protocols should be clear if post-treatment assessments are to be considered in determination of best overall response. Protocols must specify how any new therapy introduced before progression will affect best response designation. The patient’s best overall response assignment will depend on the findings of both target and nontarget disease and will also take into consideration the appearance of new lesions. Furthermore, depending on the nature of the trial and the protocol requirements, it may also require confirmatory measurement. Specifically, in nonrandomized trials where response is the primary endpoint, confirmation of PR or CR is needed to deem either one the “best overall response”.

The best overall response is determined once all the data for the patient is known. Best response determination in trials where confirmation of CR or PR IS NOT required: Best response in these trials is defined as the best response across all time points (for example, a patient who has SD at first assessment, PR at second assessment, and PD on last assessment has a best overall response of PR). When SD is believed to be best response, it must also meet the protocol specified minimum time from baseline. If the minimum time is not met when SD is otherwise the best time point response, the patient’s best response depends on the subsequent assessments. For example, a patient who has SD at first assessment, PD at second and does not meet minimum duration for SD, will have a best response of PD. The same patient lost to follow-up after the first SD assessment would be considered unevaluable.

Target Lesions	Nontarget Lesions	New Lesions	Overall Response
CR	CR	No	CR
CR	Non-CR/non-PD	No	PR
CR	Not evaluated	No	PR
PR	Non-PD or not all evaluated	No	PR
SD	Non-PD or not all evaluated	No	SD
Not all evaluated	Non-PD	No	NE
PD	Any	Yes or No	PD
Any	PD	Yes or No	PD
Any	Any	Yes	PD

Abbreviations: CR, complete response; NE, not evaluable; PD, progressive disease; PR, partial response; SD, stable disease.

Note: When nodal disease is included in the sum of target lesions and the nodes decrease to “normal” size (<10 mm), they may still have a measurement reported on scans. This measurement should be recorded even though the nodes are normal in order not to overstate progression should it be based on increase in size of the nodes. As noted earlier, this means that patients with CR may not have a total sum of “zero” on the eCRF.

In trials where confirmation of response is required, repeated ‘not evaluable (NE)’ time point assessments may complicate best response determination. The analysis plan for the trial must address how missing data/assessments will be addressed in determination of response and progression. For example, in most trials it is reasonable to consider a patient with time point responses of PR-NE-PR as a confirmed response.

